6.1. Study Intervention(s) Administered

Table 1 Study Interventions

Intervention Name	RSVpreF	Placebo	RSV-A Memphis 37b virus]
Type	Biologic	Other	Virus
Dose Formulation	The active ingredients in RSVpreF are 2 stabilized RSV prefusion F antigens, in equal amounts from virus subgroups A and B, in a lyophilized dosage form for reconstitution. The drug product is supplied as a lyophilized white cake in a 2-mL glass vial, with a 13-mm lyophilization stopper, aluminum overseal, and flip-off cap. The drug product will be reconstituted by a diluent consisting of sterile water in a prefilled syringe (PFS).	Placebo will be a lyophile match to the vaccine, which will consist of excipients matched to those used in the RSVpreF formulation, minus the active ingredients. The physical appearance of the reconstituted RSVpreF and placebo will be matched, and the study will be conducted in a double-blinded manner.	Cryovial, Liquid
Unit Dose Strength(s)	120mcg vial	0.5mL/vial	The inoculum virus titre is determined in an infectivity (plaque) assay, the titre is reported in plaque forming units per mL (PFU/mL). The challenge dose is approximately $4.5\log_{10}$ PFU.
Dosage Level(s)	A single unit dose of 120 mcg RSVpreF will be reconstituted with sterile water for an 0.5 mL injection volume	The fill volume of the placebo vial and diluent prefilled syringe is designed that the intended dose is delivered in a 0.5 mL injection volume.	A single dose of virus will be delivered. Dose volume delivery method is provided in the Analytical Plan (AP).
Route of Administration	Intramuscular injection in left arm	Intramuscular injection in left arm	Intranasal
Use	Experimental reference article	Placebo control	Infectious challenge agent

IMP and NIMP	IMP	IMP	NIMP challenge virus
Sourcing	[REDACTED]	[REDACTED]	[REDACTED]
Packaging and Labelling	The details of the study intervention packaging and labelling will be provided in the study-specific Pharmacy Manual.	The details of the study intervention packaging and labelling will be provided in the study-specific Pharmacy Manual.	RSV Challenge Inoculum will be provided in vials. The details of the virus challenge agent packaging and labelling will be provided in the AP
Current/Former Name(s) or Alias(es)	n/a	n/a	n/a

All supplies indicated in Table 6.1 will be provided per the "Sourcing" row depending upon local country operational requirements. If local sourcing, every attempt should be made to source these supplies from a single lot/batch number where possible (e.g. not applicable in the case where multiple lots or batches may be required due to the length of the study).

Refer to [Section 6.2](#) and the pharmacy manual for details regarding administration of the study intervention.

6.2. Preparation/Handling/Storage/Accountability

6.2.1. Investigational Product

RSVpreF (PF-06928316) will be supplied in single use vials at a dose level of 120 mcg/vial powder for reconstitution for injection. Placebo will be supplied in single use vials of powder for reconstitution for injection. Bulk supplies of the Investigational product will be stored at [REDACTED] Pharmacy. The IMP must be stored according to the manufacturer's instructions.

Individual participant kits will be prepared by unblinded pharmacist for reconstitution with sterile Water for Injection (sWFI) and dispensing at site. A Qualified Person (QP) will release and deliver the Investigational product to hVIVO prior to administration of the vaccine to the participant. [REDACTED] Pharmacy and hVIVO will maintain drug accountability as detailed in the study-specific Pharmacy Manual. The Investigator will ensure that all supplies are received by a responsible person, all deliveries and returns are documented and signed for, and the condition of study vaccine/placebo is monitored. Accountability records will be available for verification by the Study Monitor at each monitoring visit. At the completion of the study, there will be a final reconciliation of all study vaccine/placebo.

6.2.2. Challenge Virus

The RSV-A Memphis 37b challenge virus was produced via a nasal aspirate collected from a paediatric patient infected with RSV. The Challenge Virus stock, RSV-A Memphis 37b, was manufactured under current good manufacturing practices (cGMP). The Challenge Virus stock has undergone quality testing

hVIVO template identifier: (G_0687) v3.0

performed during manufacturing (identity, appearance, sterility, infectivity, and contaminants) according to pre-determined specifications, and has subsequently also passed an extensive panel of adventitious agent testing. The Challenge virus is stored in a secure -80 °C freezer (normal temperature range -60 °C to -90 °C).

Challenge Virus inoculum will be prepared according to the hVIVO Analytical Plan (AP) and administered in accordance with hVIVO's standard operating procedures (SOPs). Each participant will be allocated a unique vial containing the Challenge Virus and will receive the inoculum intranasally.

The time from the Challenge Virus inoculum thawing to inoculation should be no longer than 2 hours. All administrations will be made by a member of the clinical team and witnessed by a second member of the team. The exact time of inoculation will be recorded in the administration log. Accurate records will be kept of when and how much study inoculum is prepared and used. The oversight process will be signed off prior to administration of the Challenge Virus. Any non-compliance or problems with the inoculation will be recorded in the participant's source notes and reported to the PI.

Following inoculation, participants will be closely observed specifically for potential allergic reactions and any AEs for the following 24 hours. Post inoculation participants will lie flat for 10 min then sit up with nose pegs on for 20 min. Participants will continue to be monitored throughout the clinical phase of the study.

All study interventions:

1. The Investigator or designee must confirm appropriate temperature conditions have been maintained during transit for all study intervention received and any discrepancies are reported and resolved before use of the study intervention.
2. Only participants enrolled in the study may receive study intervention and only authorised site staff may supply or administer study intervention. All study intervention must be stored in a secure, environmentally controlled, and monitored (manual or automated) area in accordance with the labelled storage conditions with access limited to the Investigator and authorised site staff.
3. The Investigator, institution, or the head of the medical institution (where applicable) is responsible for study intervention accountability, reconciliation, and record maintenance (i.e., receipt, reconciliation, and final disposition records).
4. Disposal of used and unused Challenge Virus inoculum vials will be in accordance with hVIVO's SOPs.
5. Unless specifically instructed by Sponsor, the Investigator will not destroy any partly used or unused IMP supply. On written authorisation from the Sponsor, the Investigator will send unused and partly used IMP supplies and any empty containers for destruction to the address provided at the time of authorisation. Alternatively, the destruction of unused and partly used drug supplies and any empty containers may be facilitated by the Investigator using a partner service, according to local procedures, and a destruction certificate will be provided.

6.3. Randomisation and Blinding

hVIVO assigns a unique 6 digit number to each participant in the hVIVO database. This number will be used to identify a participant up to the point of randomisation, on source documents, on all study correspondence and in the study database. A separate randomisation number will be allocated to the participants at randomisation and will be used for allocation of study intervention (RSVpreF or Placebo).

The randomisation number encodes the participant's assignment to receive RSVpreF or Placebo in a 1:1 ratio.

Randomisation numbers will be assigned sequentially in ascending order; and once assigned, that randomisation number shall not be reassigned. The study site will keep a log of the randomisation number assigned to each participant.

A designated unblinded statistician, separate from the conduct or analysis of the study, will be responsible for the computer-generated randomisation schedule. Sealed copies of the randomisation code will be stored in a secure location.

Randomisation numbers will follow a 3-digit format e.g., [001]. Participants who are replaced as per [Section 7.4](#) will be replaced and assigned a new, unique randomisation number equaling the randomisation number of the replaced participant, plus 100. This will ensure that the replacement participant receives the same allocated, blinded treatment as the participant who is being replaced.

A copy of the randomisation code list will be sent to the unblinded pharmacist preparing the study intervention, so that study intervention/placebo can be prepared for each participant as appropriate. An independent Statistician [REDACTED] will prepare the randomisation schedule, and the IMP Manufacturer's pharmacist/designee [REDACTED] will prepare the participant level IMP doses in line with the randomisation schedule.

Each participant will be dispensed blinded study intervention, labelled with his/her unique randomisation number, throughout the study. With the exception of the unblinded pharmacist, the unblinded statistician preparing the randomisation code list and the Quality Assurance (QA) auditors where necessary, the Investigator and all other clinical and non-clinical staff, (including the Study Statistician, data management staff), and the participants will remain blinded to the treatment allocation until after the database has been locked and approval for study unblinding has been given.

Following database lock, on receipt of authorisation from the Sponsor, a copy of the randomisation code list will be provided to the Study Statistician to conduct study unblinding prior to analysis.

The PI/Investigator will be provided with a tamper evident sealed envelope containing details of the treatment for each participant. All opened and unopened envelopes will be collected or destroyed after the end of the study, as agreed with the Sponsor.

Individual emergency code break envelopes will be provided to the PI/Investigator should it be necessary to break the blind for a participant. The Investigator will ensure there is an appropriate procedure in place to allow access to the code break envelopes in case of an emergency arising during the quarantine period, as per hVIVO's standard operating procedures (SOPs). An emergency means that the relevant medical decision on the further care of a participant is dependent on the actual identity of the study treatment that the participant has received.

The emergency code break envelopes will contain details of the treatment for each participant.

When the code break envelope is opened, the Investigator must note the date, time, reason for unblinding and the details of the investigator and or designated site staff that broke the blind and record this information according to hVIVO SOPs. The Investigator must also immediately notify the Sponsor's Medical Monitor (SMM) that the code has been broken. If possible, the Sponsor should be consulted before the code is broken, but this will only occur if the safety of the participant will not be compromised.

Even if the code is broken, blood samples for safety, efficacy and other assessments will continue to be drawn for the remainder of the planned study period following the last dose as long as doing so will not compromise participant welfare.

The study intervention must be discontinued after unblinding, but the participant will be followed up until resolution of any AEs.

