7.4. Participant Replacement Strategy

Participants who have been vaccinated but not inoculated may be replaced in order to achieve the planned evaluable number of participants if deemed appropriate by the PI and with the approval of the Sponsor.

The replacement participant will be assigned to the same group as the original (discontinued) participant. The replacement participant will be assigned a new, unique randomisation number equaling the randomisation number of the replaced participant, plus 100; for example, participant 001 would be replaced by participant 101). This will ensure that the replacement participant receives the same allocated blinded treatment as the participant who is being replaced.

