10.3.11. Pregnancy

If a female participant or partner of a male participant becomes pregnant during the course of the study, this must be reported by the Investigator to the SMM and Study Monitor by telephone as soon as possible, in accordance with hVIVO's SOPs, and at the latest within 24 hours of becoming aware of the event.

Following the telephone notification, the Investigator must fully and accurately complete the appropriate pregnancy reporting form, which must be e-mailed to the SMM and the Study Monitor at the latest within 24 hours of becoming aware of the pregnancy.

Participants will be advised to contact their GP or a specialist, as appropriate.

Consent for follow-up of the pregnancy and pregnancy outcome will be sought from the pregnant study participant or the pregnant partner of the male study participant as applicable. Consent for follow-up will be documented on an hVIVO Pregnancy Follow-up ICF.

Provided that the appropriate consent is in place, information related to the pregnancy will be collected as per hVIVO's SOPs and the Sponsor's requirements. The completed reporting form(s) will be sent to the Sponsor for review and assessment, and subsequent reporting as required.

- A complete evaluation will be documented in the source data to permit transfer to the clinical database.
- The emergency code break envelopes will be requested (Section 6.3) to break the blind for the appropriate study participant to ensure that further care can be based on the actual identity of the study treatment that the participant received.
- hVIVO will maintain contact with the participant for a protracted period of time, but certainly until after the birth, in order to assess for outcomes that may be reportable as related AEs, and for reporting to the Sponsor as appropriate.
- hVIVO in consultation with the participant will keep the participant's GP informed.
- All cases of foetal drug exposure via the parent as a study participant will be reported to the Sponsor and the REC.

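### The plus-100 replacement number lets a code break on one participant reveal the arm of that person's replacement before enrolment

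*Combined protocol and SAP*

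**What the plan says.** Section 6.3 states that a replacement is "assigned a new, unique randomisation number equaling the randomisation number of the replaced participant, plus 100", and adds: "This will ensure that the replacement participant receives the same allocated, blinded treatment as the participant who is being replaced". Section 7.4 repeats the rule, gives the example that "participant 001 would be replaced by participant 101", and defines who is eligible: "Participants who have been vaccinated but not inoculated may be replaced". Replacement is on the principal investigator's judgement and needs Sponsor approval. The synopsis is looser and says only that the replacement will usually receive the same intervention.

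On who holds the information, Section 6.3 says: "The study site will keep a log of the randomisation number assigned to each participant". It also gives the investigator an individual code-break envelope for each participant. After a code break, "The study intervention must be discontinued after unblinding, but the participant will be followed up until resolution of any AEs".

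Pregnancy is a discontinuation reason in Section 7.2. Section 10.3.11 adds: "The emergency code break envelopes will be requested (Section 6.3) to break the blind for the appropriate study participant".

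Against this, Section 6.3 commits the investigator and all other clinical staff to remain blinded until database lock. The only exceptions are the unblinded pharmacist, the statistician who prepares the list and, where needed, QA auditors. Section 9.4.1 likewise denies the investigator access to the allocation until study end.

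**The concern.** The numbering rule is printed in the protocol and the site keeps the log, so blinded staff can see which two people share an arm. That is harmless while both codes are closed. Once the first person's code is opened, the second person's arm is known as well, although nobody has opened the second envelope.

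If the code break comes before the replacement enters, allocation concealment is lost for that person. The principal investigator, who may have opened the envelope, also helps decide whether to replace, and would know the arm being filled. The investigator then goes on to grade physical findings (Section 8.6), judge AE causality (Section 10.3.6.5) and decide on discharge or a longer quarantine stay (Section 4.1) for someone whose arm is known.

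**Working it through.** The point rests on how the rules combine rather than on a stated figure, so the check sets them side by side and then sizes the effect.

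1. **Is the pairing visible?** Take original numbers as running from 001 to 072, the maximum vaccinated in Section 9.2. Adding 100 gives 101 to 172. With the extra enrolment allowed in Section 9.7 (up to 5 per arm, so 72 + 10 = 82), the ranges are 001 to 082 and 101 to 182. No number falls in both ranges in either case. A number above 100 therefore marks a replacement and identifies the person replaced without ambiguity.

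2. **Can a code be broken between vaccination and challenge in someone who may be replaced?** Yes. Section 8.14.3 requires a serum pregnancy test in all female participants on admission to quarantine, which is after vaccination and before challenge. A positive result is a discontinuation reason (Section 7.2) and prompts a code-break request (Section 10.3.11). That person is vaccinated but not inoculated, which is the group Section 7.4 allows to be replaced. The emergency procedure in Section 6.3 names the quarantine period; the pregnancy trigger is not confined to it.

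3. **Order of events.** Suppose participant 014 is in that position and the envelope is opened. Vaccination precedes challenge by about 28 days, so replacement 114 would be a new enrolment for a later quarantine group. Site staff who learned the code for 014 would know the arm of 114 before 114 is enrolled, vaccinated, challenged or assessed. If 014 had been replaced for another reason and the code were broken later, 114 would be exposed only from that time.

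4. **Is there a safeguard?** Sections 6.3, 7.2, 7.4, 9.7 and 10.3.11 do not bar a linked replacement after a code break, hide the pairing from the site, or keep staff who know the code away from the replacement.

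5. **Size.** The documents give no code-break rate. Assuming 0 to 2 code breaks followed by a linked replacement:
   - one person is 1/31 = 3.2% of an arm, or 1/62 = 1.6% of those challenged;
   - two people in the same arm are 2/31 = 6.5% of that arm, or 2/62 = 3.2% of those challenged.

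6. **What does the same-arm link buy?** It keeps the arms equal. Effective size per arm is 2 × n1 × n2 / (n1 + n2).
   - 31 v 31: 2 × 31 × 31 / 62 = 31.
   - 32 v 30 (one replacement falls in the other arm): 1920 / 62 = 30.97.
   - 33 v 29 (two fall in the other arm): 1914 / 62 = 30.87.

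   For the few replacements at issue, exact same-arm matching is worth less than 0.5% of effective sample size.

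**The case against.** The strongest reply is that the event is rare and already has some control. It needs a code break in a short window, then a discretionary replacement by a new enrolment. An already vaccinated reserve may be the more natural way to fill the place. Replacement also needs Sponsor approval, and Section 6.3 requires the Sponsor's Medical Monitor to be told at once of any code break, so the approving side would know. Code-break handling follows site procedures that are not in the documents, so how many staff would learn the arm is unknown. All of this stands and limits the size of the point. None of it is a written bar, and Section 6.3 still describes the replacement's treatment as blinded.

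A reader might infer more than the documents support:

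- **That many participants are affected.** Up to 72 are vaccinated for 62 challenged, and 10/62 = 16%. But those 10 are planned over-vaccination. Section 7.2 describes reserves who may never be challenged, and no text gives them linked numbers. Only a Section 7.4 replacement receives one, and the documents do not say how many there will be.
- **That the symptom endpoints are directly biased.** The code break informs site staff, not the replacement. The replacement completes the diary cards (Section 8.11.2) and remains blinded. Viral load and infection confirmation come from PCR. Physician findings enter only the upper and lower respiratory illness definitions (Section 10.6.2), which feed tertiary endpoints. Any effect on the primary family would be indirect.
- **That a predecessor's vaccine reaction reveals the arm without a code break.** One serious adverse reaction, or severe non-serious reactions in two participants, halts RSVpreF dosing under stopping rules 3 and 4, so that route does not lead straight to a replacement. Section 2.2.1 lists general symptoms such as fatigue and headache after placebo too, so milder reactions are weak evidence of the arm.

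**Conclusion.** The point holds as a narrow gap in blinding and allocation concealment. The plus-100 rule and its printed guarantee mean that a code break on a vaccinated, unchallenged participant, followed by replacement, discloses the replacement's arm to the site staff who learned the code. That contradicts the blinding commitment in Section 6.3, and nothing in the protocol prevents it.

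The number affected is unknown. On an assumed 0 to 2 cases, each is about 3% of an arm, and zero is a realistic outcome. It is not a threat to power. The judgements exposed are whom to enrol, AE causality, graded findings and discharge. The conclusion assumes that the code break precedes the replacement's enrolment, the natural order when the pregnancy or code break is what ended participation, and that no unseen site procedure separates the staff involved. The gap is worth closing because closing it costs little.

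**What to change.** - Remove the visible plus-100 link and the site-facing guarantee of same treatment from Sections 6.3 and 7.4. Amend the replacement text in the synopsis to agree; its looser wording already differs from theirs.
- Have the unblinded statistician or pharmacist issue each replacement number from a concealed list, with no visible tie to the person replaced. The balance monitoring already in Section 9.7 can then continue to serve the target of 31 evaluable participants per arm without telling the site which arm is being filled.
- State that a participant whose code has been broken is never replaced by a linked same-arm number, but by the next unused concealed number.

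The cost is protocol wording and a randomisation list long enough to cover replacements. When a code-broken participant is replaced, the arms may end slightly unequal. At 32 v 30 or 33 v 29 the loss of effective size is negligible, but one arm would stand at 30 or 29 against the Section 9.7 target unless the unblinded statistician restores balance with later concealed numbers.

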6.4. Study Intervention Compliance

When participants are dosed at the site, they will receive study intervention and challenge virus directly from the Investigator or designee, under medical supervision. The date and time of each dose administered in the clinic will be recorded in the source documents and recorded in the case report form (CRF). The dose of study intervention and study participant identification will be confirmed at the time of dosing by a member of the study site staff other than the person administering the study intervention.

Any non-compliance or problems with the administration of the study intervention will be recorded in the participant's source notes and reported to the Sponsor if appropriate.

